
Item 4 Purpose and rationale Insert purpose, objectives and research questions/hypotheses here. If you cut and paste from another document, make sure the excerpted material answers the question
	
Insert purpose: The study is designed to examine histologic wound healing following ridge preservation using with mineralized freeze-dried bone allograft (FDBA) or mineralized bone allograft prepared via the Tutoplast process which does not involved freeze-drying. This entire protocol involves procedures that are standard care. The study is a 2-arm, parallel-design, randomized, prospective clinical trial. The test group subjects will have extraction sockets grafted with a PUROSE. This test group will be compared to an active control group using FDBA as the graft material. The null hypothesis is that there will be no significant difference in formation of new vital bone between treatment groups (primary outcome). In keeping with the protocol our study group has used several times before, the plan will be to extract non-molar teeth and graft with the test/control materials. Each subject will provide a single non-molar tooth site for study treatment. The graft material will be covered with a resorbable bovine pericardium membrane (called CopiOs). Following 12 weeks of healing, we will place the dental implant. To place a dental implant, an osteotomy (hole in the bone) is prepared into which the implant is placed. This osteotomy can be prepared with either a solid drill, in which case the bone that is removed is suctioned into the suction system, or with a hollow trephine drill into which a core of bone can be collected. The only "research procedure" being done in the current study is the collection of this bone core biopsy for histologic evaluation. The core biopsy will then be evaluated for the primary outcomes: % vital bone formation, % residual graft material, and % "CT/other" (fibrous tissue and marrow space). We will also be evaluating the following secondary outcomes using a custom measuring stent for each subject: change in ridge width; change in buccal ridge height, and change in lingual ridge height.

Item 5 Study Population(s) Being Recruited
 
In your recruitment plan, how many different populations of prospective subjects do you plan to target? Provide number: 1
	
Identify the criteria for inclusion:
	
Identify the criteria for exclusion:

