Data Analysis Plan: The primary hypothesis to be tested is whether the mean percentage of new bone observed histologically for patients receiving a mineralized cancellous PUROS graft for ridge preservation in an extraction site prior to implant placement is different than those receiving a mineralized cancellous FDDBA graft at a time point approximately 12 weeks after grafting. The distribution of new bone percentages is expected to be positively skewed, conforming to a double exponential distribution. The hypothesis will be tested using a Mann-Whitney U test. A total of 44 patients will receive treatment in a non-molar tooth site, with a minimum of 70% of patients expected to be fully compliant under the study protocol, so that the sample size available for histologic examination will be at least 14 patients per treatment group. This proposed sample size is sufficient to detect a mean difference of one standard deviation or more by Mann-Whitney U test at the 0.05 level with power of 88.5%. For example, if the population standard deviation of new bone percentage within patients is 10% or less, then the proposed sample is sufficient to detect a clinically significant mean difference of 10% or more new bone for patients receiving PUROS compared to FDDBA.

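### The stated 88.5% power is not what a two-sided Mann-Whitney U test gives with 14 patients per group: it is about 80% under the plan's own distribution and about 70% if the data are normal

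*Combined protocol and SAP*

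**What the plan says.** The Data Analysis Plan in Item 6 gives every element of a power statement except the number of sides.

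- Test: "The hypothesis will be tested using a Mann-Whitney U test".
- Distribution: "The distribution of new bone percentages is expected to be positively skewed, conforming to a double exponential distribution".
- Sample: 22 per group are recruited and at least 70% are expected to comply, so that "the sample size available for histologic examination will be at least 14 patients per treatment group".
- Power: this is "sufficient to detect a mean difference of one standard deviation or more by Mann-Whitney U test at the 0.05 level with power of 88.5" per cent.
- Example: a 10-point difference in new bone is detectable "if the population standard deviation of new bone percentage within patients is 10% or less".

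Sidedness has to be inferred. Item 6 asks whether the two means differ, without a direction, and Item 4 says "The null hypothesis is that there will be no significant difference in formation of new vital bone between treatment groups". Both point to a two-sided test.

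**The concern.** With 14 per group and a 1-SD difference, a two-sided t-test on normal data has 72.1% power. For a rank test to reach 88.5% in the same sample, the shape of the data would have to give it a very large advantage. The one distribution named cannot be pinned down, because a double exponential in the usual (Laplace) sense is symmetric and so is not positively skewed.

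This sentence is the only quantitative support for the sample size; elsewhere Item 6 merely mentions a power analysis. It also carries the claim that a 10-point difference, which the plan calls clinically significant, can be detected. If the power is overstated, a non-significant result would be read as stronger evidence of similarity between the grafts than the design can give.

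**Working it through.** **Inputs, all from Item 6:** Mann-Whitney U test; alpha 0.05, taken as two-sided; 14 analysable patients per group; pure location shift of 1 SD; double exponential parent distribution.

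**Step 1: reproduce 88.5%.** The usual shortcut multiplies n by the asymptotic relative efficiency (ARE) of the Mann-Whitney test against the t-test, then takes t-test power at d = 1. The ARE is 12σ²(∫f²)².

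- Laplace: σ² = 2 and ∫f² = 1/4, so ARE = 12 × 2/16 = 1.5. Effective n = 14 × 1.5 = 21 per group. Noncentral t with 40 df gives **88.53%**, which matches.
- Gumbel: σ² = π²/6 and ∫f² = 1/4, so ARE = π²/8 = 1.234. Effective n = 17.27, and power is 81.4%.
- Normal: ARE = 3/π = 0.955. Effective n = 13.37, and power is 70.0%.

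A second route lands on the same number: 22 × 3/π = 21.01 per group gives 88.54%. That is normal-data power with no dropout, whereas the plan attaches its figure to 14 per group. The Laplace route is the likelier source.

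**Step 2: why the shortcut fails here.** The ARE is a limit for large samples and vanishing shifts. Much of the Laplace advantage comes from its sharp central peak, and it shrinks when the groups lie a full SD apart.

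**Step 3: power of the planned test.** With 14 per group the exact two-sided test rejects when the smaller U is 55 or less (true size 0.0497). Simulated power for a 1-SD shift, with 200,000 or more replicates per case:

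| Parent distribution | 14 per group | 15 per group | 22 per group |
|---|---|---|---|
| Laplace | 80.5% | 82.1% | 94.8% |
| Gumbel | 78.0% | 79.7% | 93.4% |
| Normal | 69.9% | 71.5% | 88.2% |
| Exponential | 87.1% | 88.5% | 97.4% |

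Other positively skewed shapes at 14 per group give 76.1% (gamma, shape 4), 81.1% (gamma, shape 2) and 83.7% (lognormal, σ = 0.5). These shapes, and the exponential, are assumptions made for this check and not the plan's. Nothing tried reaches 88.5% at 14 per group.

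**Step 4: what 88.5% would require.** At 14 per group the shift must be about 1.15 SD (Laplace), 1.17 SD (Gumbel) or 1.27 SD (normal). With SD 10 that is 11.5 to 12.7 points, not 10. Holding the shift at 1 SD under Laplace, about 17 to 18 analysable patients per group would be needed (17: 87.5%; 18: 89.8%).

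**Step 5: the SD label.** Item 4 allows one site per subject, and Item 6 takes one trephine core from it. A within-patient SD cannot be estimated from such data and does not govern the comparison. The relevant SD is between patients within a group.

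**The case against.** The figure is not a slip of arithmetic. A standard method applied to the plan's n, test, effect size and named distribution returns it exactly. That is correct, and the fault is best described as an approximation unsuited to this sample. The sentence still states the power of a particular test at a particular size, and that test does not have it.

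Fourteen is a floor. Seventy per cent of 22 is 15.4, and with all 22 per group analysable the power is 94.8% under Laplace and 88.2% under normality. This softens the practical consequence, but the plan ties 88.5% to 14 per group, so the figure must be true there.

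The plan does not assume normality, so 70% is a sensitivity case and not its base case. This also stands: on either reading of double exponential the risk of a miss at 14 per group is 20 to 22%. The normal case is still worth giving, because the stated distribution contradicts itself.

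A one-sided exact test under Laplace would have about 87.7% power, close to the stated value. The hypothesis has no direction, however, and the one-sided version of the shortcut gives 93.8%, so a one-sided test does not explain the figure.

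The skewness and SD wording change little numerically: about 2 points of power between Laplace and Gumbel, and none for the SD label. They belong here because they sit in the same statement and leave its assumption undefined.

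**Conclusion.** The concern holds. At 14 per group and a 1-SD shift, the planned two-sided test has about 80% power under Laplace, 78% under Gumbel and 70% under normality. The stated figure is about 8 points too high on the plan's own assumption, or 10 if Gumbel is meant, and about 19 points too high for normal data. The risk of missing the difference is about 20 to 30%, against the implied 11.5%.

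This rests on a two-sided exact test, a pure location shift with equal spread in both groups, and retention at the floor. The design is not invalidated: under Laplace it keeps roughly the conventional 80% even at that floor. The power statement is nevertheless wrong as written and should be corrected.

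**What to change.** Keep the sample size and restate the power along these lines: with 14 analysable patients per group, a two-sided Mann-Whitney U test at the 0.05 level has about 80% power for a 1-SD difference if the data are double exponential (Laplace), and about 70% if they are normal; power of 88.5% corresponds to a difference of about 1.15 to 1.27 SD.

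Make the distribution coherent. Either drop the positive skew and keep the Laplace, or keep the skew, name the skewed distribution and quote its power (about 78% for Gumbel). State how the power was computed. Describe the SD as between patients within a group, and amend the 10-point example to carry the corrected power.

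The cost is wording only. The stated power becomes less favourable; no extra patients are needed, and the test does not change.

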**Item 7 Risks Section:**

Complete the following table to describe the risks of all **research procedures** listed in Step 2, Institutional Form (items 28-34). *Do not list risks of Routine care procedures here.*

N/A, Risks are described in the informed consent document – do not complete this table.

Research procedures
 
example:
 
 
• History and physical
 
• Questionnaire
 
• Laboratory tests
 
 
Add or delete rows as needed
	
Risks
 
List the reasonably expected risks under the following categories as appropriate:

Randomization - Ridge preservation following tooth extraction using one of 2 graft materials in preparation for dental implant 12 weeks post-grafting
	
Serious and likely;   None                      Serious and less likely;   None                      Serious and rare; This is a standard of care risk                      FDDBA may contain traces of the processing reagents Bacitracin, Gentamicin, Polymyxin B Sulfate, alcohol, and/or surfactants. Caution should be exercised if the patient has a known sensitivity or allergy to any of these antibiotics or reagents. PUROS may contain trace amounts of residual chemicals used in processing: acetic acid, acetone, hydrogen peroxide and sodium hydroxide.
 
Not serious and likely;   None                      Not serious and less likely   There is no additional research related risk involved in the use of the FDDBA or PUROS materials for ridge preservation, as there is no alteration to the clinical course or standard care treatment for this study. Each of these materials is commonly used in clinical practice. While we may indeed find that there is more new vital bone formation in one group vs. another, there is no reason to think that will impact the success of the implant that is placed. Thus, the study is definitely minimal risk. There is, of course, a hypothetical risk that disease transmission could occur with the bone graft materials but it is not quantifiable, as it has not occurred. Both materials are terminally sterilized with gamma radiation to achieve a sterility assurance level (SAL) of 10^-6.


Insert procedure here
	
Serious and likely;   Insert risk here or enter "none"                      Serious and less likely;   Insert risk here or enter "none"                      Serious and rare;   Insert risk here or enter "none"                      Not serious and likely;   Insert risk here or enter "none"                      Not serious and less likely   Insert risk here or enter "none"

Insert procedure here
	
Serious and likely;   Insert risk here or enter "none"                      Serious and less likely;   Insert risk here or enter "none"                      Serious and rare;   Insert risk here or enter "none"                      Not serious and likely;   Insert risk here or enter "none"                      Not serious and less likely   Insert risk here or enter "none"

